10.4.3 Primary Analysis

The objective of the primary analysis is to evaluate the efficacy and safety of AMG 334 in subjects with episodic migraine, compared to placebo, and to identify an optimal dose in Japanese population. The following hypothesis for the primary endpoint will be tested for each AMG 334 treatment group (140 mg, 70 mg, and 28 mg) compared to placebo using the linear mixed effects model:

- Clinical Hypothesis: In subjects with episodic migraine, AMG 334 reduces the mean monthly migraine days from baseline, compared to placebo

To maintain a family-wise type I error at 0.05, the pair-wise comparison will be tested in a sequential testing procedure in the order of AMG 334 140 mg vs. placebo, 70 mg vs. placebo and 28 mg vs. placebo. The lower dose group will be tested only when the higher dose group is considered statistically significant.

The primary analysis will be performed when the last subject completes the week 24 assessment or is discontinued from the study.

10.4.4 Final Analysis

The objective of the final analysis is to evaluate the long-term profile of migraine days and adverse events of AMG 334 in subjects with migraine after the 24-week double-blind treatment phase, **OLTP**, and safety follow-up. The final analysis for the study, including all study periods and all data, will be performed at the end of the trial. In addition to the primary analysis, efficacy data and safety data from the **OLTP**, the safety follow-up will

be tabulated by double-blind treatment group as well as by aggregated overall AMG 334 treatment group; no formal testing will be conducted.

Final Analysis activities are commenced based on achieving the End of Trial milestone described in [Section 3.6.2](#).

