The continuous efficacy endpoints will be analyzed using a linear mixed effects model including treatment group, baseline value, stratification factor, scheduled visit, and the interaction of treatment group with scheduled visit, without any imputation of missing data. The primary endpoint will be tested for each AMG 334 treatment group compared to the placebo group using appropriate contrasts in a closed testing procedure. The mean change from baseline for each treatment group, and the treatment difference, 95% confidence intervals, and p-value will be reported. For all efficacy endpoints, nominal p-values will be provided for the comparisons between each AMG 334 treatment group vs the placebo group without multiplicity adjustment.

Dichotomous efficacy endpoints will be analyzed using a stratified Cochran-Mantel-Haenszel (CMH) test after the missing data are imputed as non-response. The odds ratio for each AMG 334 treatment group vs placebo group and associated 95% confidence intervals will be reported. As safety analyses, subject incidence of treatment-emergent adverse events will be tabulated by system organ class and preferred term by treatment group for the double-blind treatment phase. For the OLTP, **exposure**-adjusted subject incidence rate of treatment-emergent adverse events will be tabulated overall. Measurements of safety laboratory and vital sign data will be summarized over time and laboratory shift tables will be provided.

The proportion of subjects who administer a full dose of AMG 334 in home-use will be summarized by treatment group at CHU day 29 and day 57. Subject incidence of adverse

events, serious adverse events, and adverse device effects will be summarized by system organ class and preferred term for subjects enrolled in the CHU substudies.

[figure not shown]
For a full description of statistical analysis methods, please refer to [Section 10](#).

Sponsor: Amgen Inc.

Data Element Standards
Version/Date:

[figure not shown]
Version 4, 31 October 2013

Study Design and Treatment Schema for Subjects That Completed Week 48 Under Protocol Amendment 2 (OL70 subjects)

[figure not shown]
IP = investigational product; QM = monthly; SC = subcutaneous

Study Design and Treatment Schema for Subjects Still in the Double-blind Treatment Phase Protocol Amendment 2
(OL140 Subjects)

IP = investigational product; QM = monthly; SC = subcutaneous

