Refer to [Section 10.1.1.4](#) for the definition of migraine day. This definition of migraine day is consistent with the diagnostic criteria of migraine and probable migraine according to ICHD-3 and is consistent with those of the 20120178 Phase 2 episodic migraine trial. The mean monthly migraine days will be calculated using monthly migraine day data from the last 3 months (months 4, 5, and 6) of the double-blind treatment phase. A migraine day will be determined based on headache and medication information entered by subjects daily into a handheld electronic device (electronic diary; eDiary).

The secondary efficacy endpoints are the 50% responder rate and mean monthly migraine-specific medication treatment days. These secondary endpoints were selected because they are highly clinically relevant and provide complementary information to the primary endpoint in the evaluation of AMG 334 as a migraine prophylactic agent.

Rationale for AMG 334 Doses

Three dose levels of AMG 334 (ie, 28 mg, 70 mg, and 140 mg) were chosen for this Phase 2 study with the intent to bridge the data from the global Phase 3 episodic migraine study (20120296). These doses were selected in order to 1) demonstrate statistically significant improvement from placebo on the primary outcome measure, and 2) to establish the dose-response relationship of AMG 334 in Japanese subjects. **In the open-label phase, the dose of AMG 334 is being increased to 140 mg in a subset**

[figure not shown]
of subjects to provide continuous 1-year safety data for subjects receiving either AMG 334 70 mg or 140 mg.

The efficacy and safety of AMG 334 (7 mg, 21 mg, and 70 mg QM SC) were evaluated for the prevention of episodic migraine in a 12-week global Phase 2 study (20120178). The study randomized 483 subjects (AMG 334 7 mg [n=108], AMG 334 21 mg [n=108], AMG 334 70 mg [n=107] and placebo [n=160], QM SC) with a history of migraine for ≥ 12 months and a monthly migraine frequency of ≥ 4 and ≤ 14 migraine days.

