In the global 12-week study 20120295, 667 subjects with chronic migraine (≥ 15 headache days per month, with ≥ 8 migraine days) were randomized to AMG 334 70 mg (n = 191), AMG 334 140 mg (n = 190), or placebo (n = 286), QM SC. For the primary endpoint of change in monthly migraine days from baseline to the last 4 weeks of the 12-week double-blind treatment phase, the 70 mg and 140 mg doses were significantly different from placebo (-6.64 days and -6.63 days vs. -4.18 days, $p < 0.001$). Treatment-emergent adverse events were reported in 39.0%, 43.7%, and 46.8% of subjects in the placebo, AMG 334 70 mg, and AMG 334 140 mg groups, respectively. No apparent dose-response pattern was observed across the most common treatment-emergent adverse events. The most commonly reported adverse events occurring in $\geq 2\%$ of all AMG 334 treated subjects were injection site pain, upper respiratory tract infection, nausea, nasopharyngitis, constipation, muscle spasms, and migraine. Serious adverse events were reported in 2.5%, 3.2%, and 1.1% of subjects in the placebo, AMG 334 70 mg, and AMG 334 140 mg groups, respectively. No individual serious adverse event was reported in more than 1 subject in the placebo, AMG 334 70 mg, or AMG 334 140 mg groups. Subjects from 20120295 were eligible to enroll in an ongoing 52-week open-label extension study (20130255), in which the original dose was 70 mg QM SC, but subsequently the dose was increased to 140 mg QM SC. Of the 609 subjects enrolled, 259 subjects received at least one dose of AMG 334 140 mg. Based on the interim analysis data cut-off of 01 September 2016 with a mean (SD) duration of exposure to AMG 334 140 mg of 176.4 (70.9) days, the reported adverse events were consistent with the known safety profile of AMG 334.

The global Phase 2 study (20120178) in episodic migraine has an ongoing open-label phase of up to 256 weeks. The original dose was 70 mg but a protocol amendment dated 07 April 2016 increased the dose to 140 mg for all subjects. Thus 140 mg has been investigated in the double-blind portions of studies 20120296 and 20120295, as well in open-label or active treatment extension phases (studies 20120296, 20130255, 20120178), and no new safety signal has been detected.

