6.2.1.1 Dosage, Administration, and Schedule

Amgen investigational product (ie, AMG 334 28 mg, AMG 334 70 mg, AMG 334 140 mg, or placebo) will be dosed monthly (QM) by subcutaneous (SC) injections. Double-blind AMG 334 140 mg, AMG 334 70 mg, AMG 334 28 mg, or placebo will be administered during the 24-week double-blind treatment phase (ie, at day 1 and weeks 4, 8, 12, 16, and 20). **During the OLTP, AMG 334 70 mg or AMG 334 140 mg QM SC will be administered, depending on the subject's visit completion status after IRB approval of Protocol Amendment 2.**

During the double-blind treatment phase, 3 SC injections are to be given for each investigational product administration (ie, at day 1 and weeks 4, 8, 12, 16, and 20) to maintain the dose-level blinding. The 3 SC injections should be separated by no more than approximately 1 minute. During the OLTP, 1 SC injection is to be given for **AMG 334 70 mg and 2 SC injections for AMG 334 140 mg. If and when 140 mg/mL pre-filled syringes become available during the open-label phase, the 140 mg dose may be administered by a single 140 mg/mL SC injection.**

After IRB approval of Protocol Amendment 2, after the 24-week double-blind treatment phase, there is a 76-week OLTP with the dose determined by the subject's week 48 status:

- (1) **Subjects who have already completed the week 48 visit will continue to receive open-label AMG 334 70 mg QM SC (OL70) for a total of 76 weeks.**
- (2) **Subjects who have not yet completed the double-blind treatment phase and are not yet in the open-label phase will receive AMG 334 140 mg QM SC (OL140) upon entering the open-label phase and continue receiving open-label 140 mg QM SC for 76 weeks.**
- (3) **Subjects who have not yet completed the week 48 visit but are in the open-label phase receiving AMG 334 70 mg QM SC must increase their dose to AMG 334 140 mg QM SC and continue receiving open-label AMG 334 140 mg QM SC until the week 100 visit (OL70-140) for a total open-label phase duration of 76 weeks. The dose increase to 140 mg should be done at the first available opportunity, defined as the first visit after IRB approval of Protocol Amendment 2. At the time of the dose increase, the End of Open-label 70 mg eCRF page will need to be completed as subjects will be transitioning from 70 mg to 140 mg.**

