As a result of Protocol Amendment 2, there will be 3 possible dose sequences in the open-label phase, depending on completion of week 48 visit as noted above: (1) subjects receiving only AMG 334 70 mg QM SC in the open-label phase (OL70), (2) subjects receiving only AMG 334 140 mg QM SC in the open-label phase (OL140), and (3) subjects receiving both AMG 334 70 mg (for up to 24 weeks) and 140 mg QM SC (OL70-140). Subjects assigned to receive AMG 334 140 mg QM SC during the open-label phase will not have the option to decrease open-label AMG 334 from 140 mg QM to 70 mg QM.

The anatomical sites for administration of investigational product are the upper arm, upper thigh, or abdomen. Please see the IPIM for investigational product details.

Following the first 3 doses of investigational product in the double-blind treatment phase (ie, day 1, week 4, week 8), subjects are to remain in the clinic for approximately 1 hour for observation.

During the CHU substudy, the subject will self-administer IP (1 or 2 injections using Al/pen) under site supervision on day 1. On day 28 and day 56 during the CHU substudy, the site will provide IP to the subject to self-administer (1 or 2 injections using Al/pen) on the next day. The anatomical sites for self-administration are the upper thigh or abdomen. The upper arm should only be used if administered by a care-giver. During the CHU substudy the injection site location should be the same for all injections but do not use the same spot on the injection site you used for a previous injection. For further details regarding self-administration procedures, the IFU should be consulted.

Overdose with this product has not been reported.

Only authorized investigational site study staff members are to administer Amgen investigational product.

The quantity, start date, and box number of investigational product are to be recorded on each subject's CRF.

If a subject is enrolled in the CHU substudy, the box number provided to the subject and information obtained at telephone visits should be recorded by the site on each subject's CRF, as described in [Section 7.2.25](#).

The dosing schedule is described by a [schema](#) in the protocol synopsis.

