10.1.2 Analysis Sets

The full analysis set (FAS) includes all subjects who were randomized in the study. The efficacy analysis set includes subjects in the FAS and who received at least one dose of investigational product and **had** at least one **change from baseline measurement in** monthly migraine days **during** the double-blind treatment phase. In the efficacy analysis set, subjects will be analyzed according to randomized treatment, regardless of the treatment received. The per-protocol set is a subset of the efficacy analysis set that includes subjects who completed the 24-week double-blind treatment phase with no major protocol violations. For safety endpoints, all randomized subjects who received at least one dose of investigational product (ie, safety analysis set) will be analyzed **according to the randomized treatment unless a subject has received the incorrect dose during the entire double-blind treatment phase.** The open-label analysis set (OLAS) will consist of all subjects receiving at least one dose of AMG 334 in the **OLTP**. This analysis set will be used when summarizing data collected during the **OLTP**.

All subjects enrolled in the CHU substudy will be included in the CHU substudy analysis set.

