10.5.5 Safety Endpoints

For safety endpoints, all randomized subjects who received at least one dose of investigational product (ie, safety analysis set) will be analyzed **according to the randomized treatment unless a subject has received the incorrect dose during the entire double-blind treatment phase.**

The Medical Dictionary for Regulatory Activities will be used to code all adverse events.

Subject incidence rates (double-blind treatment phase) and **exposure-adjusted** subject incidence rates (**OLTP**) of all treatment-emergent adverse events will be tabulated by treatment groups and by system organ class and preferred term. Tables of fatal adverse events, serious adverse events, adverse events leading to withdrawal from investigational product, treatment-related adverse events, serious treatment-related adverse events, and adverse events of special interest also will be provided.

In addition, summaries of treatment-emergent adverse events and summaries of serious treatment emergent adverse events will be provided by preferred term in descending order of frequency. The analyses of safety laboratory endpoints will include summary statistics over time by treatment group **for selected analytes**. Shift tables of the worst on-study safety laboratory toxicity based on grade relative to baseline will be tabulated by treatment group.

The analyses of vital signs will include summary statistics over time by treatment group.

The incidence and percentage of subjects who develop anti-AMG 334 antibodies (binding and if positive, neutralizing) at any time will be tabulated by treatment group.

All safety analyses will be performed for the double-blind treatment phase and **OLTP** separately.

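### No main-study open-label adverse-event table is specified by open-label dose or sequence, although Amendment 2 raised the dose to obtain one-year safety data at 70 mg or 140 mg

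*Protocol*

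**What the plan says.** **Purpose.** Protocol 2.3 (Rationale for AMG 334 Doses) says the open-label dose is being raised in a subset "of subjects to provide continuous 1-year safety data for subjects receiving either AMG 334 70 mg or 140 mg".

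**Sequences.** Protocol 6.2.1.1 says that, as a result of Amendment 2, "there will be 3 possible dose sequences in the open-label phase": OL70, OL140 and OL70-140. Which one applies depends on the visits completed when the IRB approves the amendment. When a subject moves from 70 mg to 140 mg, "the End of Open-label 70 mg eCRF page will need to be completed".

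**Tables in the current protocol.** Three places describe the open-label grouping:

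- Section 10.4.4: efficacy and safety data will "be tabulated by double-blind treatment group as well as by aggregated overall AMG 334 treatment group".
- Synopsis, Statistical Considerations: the exposure-adjusted "subject incidence rate of treatment-emergent adverse events will be tabulated overall".
- Section 10.5.5: incidence rates (double-blind) and exposure-adjusted rates (open-label) "of all treatment-emergent adverse events will be tabulated by treatment groups and by system organ class and preferred term".

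**SAP.** SAP 1 ties the plan to Protocol 1.0 of June 2015. SAP 3.1.2 describes a 52-week open-label phase at 70 mg only. SAP 10.1 analyses subjects by randomised group, and SAP 10.6.1 presents all adverse-event tables by treatment group. In SAP 6.6, neither the open-label exposure duration nor the exposure-adjusted rate has a cut at a dose increase. The names OL70, OL140 and OL70-140 do not appear.

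**The concern.** The amendment changed the open-label dose in order to produce a particular body of safety data, but the stated grouping of the open-label tables does not show it. A double-blind column describes what a subject received before week 24. It does not identify the open-label dose, because the sequence was set by visit timing. The overall column mixes all doses by construction.

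One-year safety at each dose could therefore be collected as intended and still not be visible in the tables as written. The protocol's other evidence does not replace it. The placebo-controlled comparisons in Section 2.3 cover 12 to 24 weeks, and the open-label 140 mg exposure reported there for the chronic migraine extension averages 176.4 days.

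**Working it through.** **1. Can the one-year figure be reproduced from the schedule?**

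Inputs: the open-label phase runs from week 24 to week 100, 76 weeks (Protocol 6.2.1.1). Doses fall every 4 weeks from week 24 to week 96 (schedule footnotes). OL70-140 subjects have up to 24 weeks at 70 mg, so the increase falls at a visit *s* between week 28 and week 48.

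- Open-label doses: (96 − 24)/4 + 1 = 19.
- Doses at 70 mg in OL70-140: (*s* − 24)/4. Doses at 140 mg: 19 − (*s* − 24)/4.
- Weeks at 140 mg in OL70-140: 100 − *s*.

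| Sequence | 70 mg doses | 140 mg doses | Weeks at 140 mg | Share of 76 weeks |
|---|---|---|---|---|
| OL70 | 19 | 0 | 0 | 0% |
| OL70-140, *s* = 48 | 6 | 13 | 52 | 52/76 = 68% |
| OL70-140, *s* = 28 | 1 | 18 | 72 | 72/76 = 95% |
| OL140 | 0 | 19 | 76 | 100% |

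The latest increase gives 100 − 48 = 52 weeks, so one year is reproduced, but only nominally. Open-label visits may move by 4 days either way (Protocol 7). An increase 4 days late with a final visit 4 days early leaves 52 × 7 − 8 = 356 days. Missed doses are not made up (Protocol 6.2.1.2).

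**2. Does a planned column isolate one dose?**

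Nothing ties sequence to randomised arm, so any of the four double-blind columns can hold all three sequences. Within one column, completers can have 0, 13 to 18, or 19 of 19 open-label doses at 140 mg.

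The documents give no sequence counts, so the actual mix is unknown. As an illustration with *assumed* shares, the proportion of open-label person-weeks at 140 mg is [p(OL140) × 76 + p(OL70-140) × w]/76, with w from 52 to 72:

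| Assumed OL70 / OL140 / OL70-140 | Person-weeks at 140 mg |
|---|---|
| 80 / 10 / 10% | 17% to 20% |
| one third each | 56% to 65% |
| 10 / 80 / 10% | 87% to 90% |

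In none of these mixes is the column a single dose.

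**3. Does the SAP split time at the increase?**

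SAP 6.4 ends a completer's open-label safety window 112 days after the last open-label dose: week 96 + 16 = week 112, which is 88 weeks from week 24. In OL70-140 the part from the increase onward is 112 − *s* = 64 to 84 weeks, or 64/88 = 73% to 84/88 = 95%. SAP 6.6 has no rule for separating this from the preceding 4 to 24 weeks at 70 mg, or for assigning an event to the dose at onset.

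**4. Do other planned outputs fill the gap?**

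- Exposure summaries (Protocol 10.5.1, SAP 10.6.7) can describe the dose mix but contain no events.
- The home-use substudy has about 50 subjects, excludes those on open-label 70 mg (Protocol 4.2), ends at day 85 and has its own analysis plan.
- Exposure-response work is in a separate plan (SAP 10.7.1) that is not among the documents, so it cannot be counted either way.

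**The case against.** The strongest reply is that the documents do not rule these tables out. Protocol 10.5.1 leaves method detail to the SAP, and the SAP supplied is tied to Protocol 1.0, so its silence reflects its version and is not a decision. Section 10.5.5 governs the open-label adverse-event rates, and its undefined term could be read as open-label dose group. This stands. A reader might infer that the sponsor has decided against tables by dose, and that cannot be supported. What can be said is that none is specified in the documents supplied. The Section 10.5.5 sentence also covers the double-blind phase, where the same words must mean the randomised arms, and Section 10.4.4 and the Synopsis name only other groupings.

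Four further limits also stand:

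- The purpose in Section 2.3 concerns safety. A reader might extend the point to efficacy and patient-reported outcomes, but the exploratory long-term objective, which covers maintenance of effect, is not dose-specific, and the existing tables answer it.
- A reader might add up 140 mg doses over both phases to show how misleading a column label is. Section 10.5.5 analyses the phases separately, so no planned adverse-event table would show that total.
- The open-label analysis set ("The open-label analysis set (OLAS) will consist of all subjects receiving at least one dose of AMG 334 in the" open-label phase) only defines a population. It does not by itself merge doses; the table columns do.
- The randomised-treatment rule in SAP 10.6 names the Safety Analysis Set, which SAP 7.3 uses for the double-blind phase, so its reach into the open-label phase is unclear. Its exception is for an incorrect dose, and a planned open-label dose is not one.

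The open-label output is also descriptive, and the dose change is recorded, so the tables could be produced later without loss of data. That lowers the stakes but does not reconcile the text.

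**Conclusion.** The point holds in limited form. The current protocol states groupings for the open-label adverse-event data that do not show what the dose increase was meant to provide, and its three statements do not agree. The available SAP cannot resolve this because it assumes one open-label dose.

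The size is known only per subject: nominally 0, 13 to 18, or 19 of 19 open-label doses at 140 mg within the same double-blind column. These counts assume completers dosed on schedule. How mixed each column would be depends on sequence counts that the documents do not give, and the percentages under assumed shares are illustrations only.

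A reader might infer that adverse-event rates differ between 70 mg and 140 mg, or that the mixing hides a signal. The documents do not support that. For the 12-week chronic migraine study, Section 2.3 reports: "No apparent dose-response pattern was observed across the most common treatment-emergent adverse events". Nor should the 52 weeks be read as guaranteed for every completer, given visit windows and missed doses.

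This is a low-cost improvement to descriptive safety reporting. Primary, secondary and double-blind safety results are not affected.

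**What to change.** 1. **Protocol.** Reconcile the Synopsis, 10.4.4 and 10.5.5 so that they give the same grouping, and define *treatment groups* for the open-label phase.
2. **SAP, when updated to Amendment 2.** Keep the tables by randomised group and overall. Add descriptive open-label exposure and adverse-event tables by sequence (OL70, OL140, OL70-140).
3. **SAP 6.6 and 10.6.1.** Add exposure-adjusted adverse-event rates by dose at event onset, with OL70-140 person-time split at the recorded dose-increase date.
4. **Labelling.** Mark the new tables as non-randomised and descriptive, since sequence follows visit progress at IRB approval.
5. **Optional.** Efficacy and patient-reported outcome tables by sequence.

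The cost is a short protocol clarification, a SAP update that Amendment 2 calls for in any case, and extra table shells. No new data are needed, because the change of dose is already captured on its own eCRF page. The downside is more output that supports description only.
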